7.5.10. Serious Adverse Event Reporting

All SAEs should be reported via the "SAE Report Form" to PTC Therapeutics within 24 hours of becoming aware of the event(s). In addition, the AE portion of the eCRF must also be completed in EDC.

The SAE report form should be signed by the investigator; however, if the investigator is unable to sign at the time of the event or within 24 hours, the form should be signed by the clinical staff member reporting the SAE (eg, the study coordinator). The SAE report form must be faxed or e-mailed to the PTC Therapeutics Pharmacovigilance Department or designee and to the site Institutional Review Board/Ethics Committee IRB/EC (if required by local regulations) within 24 hours.

Follow-up information to the SAE should be clearly documented with "Follow-up" box checked and the follow-up number in the SAE Report Form completed and faxed or e-mailed to the same party. All follow-up SAE report forms for the event must be signed by the investigator. Any source documents (eg, progress notes, nurses' notes, laboratory and diagnostic test results, discharge summaries) provided to the sponsor should be redacted so that the subject's name, address, and other personal identity information are obscured. Only the subject's study number and initials are to be provided (in regions where the provision of such information is permitted). The information in the AE portion of the eCRF and the SAE report form(s) must match or be reconciled. Where the same data are collected, the information on the SAE Report Form must be completed in a consistent manner.

In the rare event that the investigator does not become aware of the occurrence of an SAE immediately (for example, if a subject initially seeks treatment elsewhere), the investigator is to report the event within 24 hours after learning of it and to document his/her first awareness of the AE.

The PTC Therapeutics Pharmacovigilance Department contact information for reporting SAEs is provided below. This information is also provided in the Study Manual and in the SAE report form.

PTC Therapeutics Safety Department

Attention: Pharmacovigilance

E-mail:

Facsimile:

7.5.11. Reporting Pregnancy

PTC Therapeutics should be notified in the event that a female subject in the study, or a female partner of a male subject in the study, becomes pregnant on-study or within 50 days of the last administration of study drug must be reported on an electronic form "Investigational and Marketed Products Pregnancy Report Form" (see study manual for details).

This must be done whether or not an AE has occurred and within 24 hours of awareness of the pregnancy. The information submitted should include the anticipated date of birth or pregnancy termination.

Written consent is required prior to collecting and reporting any information on a female partner of a male subject in the study.

If possible, the investigator should follow the subject, or the pregnant female partner of a male subject, until completion of the pregnancy and notify the medical monitor of the outcome within 5 days or as specified below. The investigator will provide this information with 'Follow-up' box checked and the follow-up number completed on the Pregnancy Report Form (see the study manual for details).

If the outcome of the pregnancy meets the criteria for immediate classification as an SAE (ie, preterm termination, elective abortion, intrauterine death, or other), the investigator should follow the procedures for reporting SAEs, ie, report the event to the PTC Therapeutics Safety Department or designee and follow-up by submission of appropriate AE eCRFs (see Section 7.5.10).

7.5.12. PTC Therapeutics Adverse Event Reporting Requirement

As the sponsor of the study, PTC Therapeutics is responsible for reporting certain safety information, particularly AESIs, SAEs and subject deaths related to participation in the study, to each investigator in an expedited manner. If notification of an AE requiring expedited reporting to investigators is received, PTC Therapeutics or its designated representative will contact each investigational site participating in this study by e-mail, fax, and/or overnight mail such that the investigator can promptly notify the site IRB/EC per their local requirements. The initial expedited safety report will be provided as required according to local regulations (eg, within 15 days) after the earliest date PTC Therapeutics or an agent of PTC Therapeutics (eg, a site monitor) becomes aware of an AE. This awareness date is the date the regulatory reporting clock begins, and the date is considered Day 0.

8. STATISTICAL CONSIDERATIONS

A statistical analysis plan (SAP) will be prepared and approved prior to the first unblinded interim analysis to provide a more detailed description of the nature of the analyses and the manner in which results will be compiled. The SAP will include details of the statistical models to be used and the test statistics to be employed.

8.1. Statistical Hypotheses

The null hypothesis for the primary efficacy comparison is that the distribution of time to respiratory improvement in hospitalized subjects with COVID-19 is the same between the 2 groups of PTC299 and placebo. The alternative hypothesis is that the distribution of time to respiratory improvement between the 2 treatment groups is not the same. Rejecting the null hypothesis with shortened time to respiratory improvement in the PTC299, for the intent-to-treat (ITT) population, will be considered a successful demonstration of efficacy.

8.2. Sample Size Determination

This is a group sequential design with 2 interim analyses planned. The first interim analysis will only assess the safety and the trial will not be stopped for futility or superiority of efficacy. It will be performed after the first 40 randomized subjects have completed Day 28 or discontinued due to death, withdrew consent, or were lost-to-follow-up.

The second interim analysis is to assess futility and will be performed when 50% of respiratory improvement events have been reached, ie, 163 events have been observed (approximately 190 subjects). Lan-DeMets beta spending function (non-binding option) is used to define the boundary for the 2nd interim futility analysis and the final analysis to ensure the overall beta of 80%. The sample size was calculated to reflect the primary endpoint of time from randomization to respiratory improvement, which is defined as the time from randomization to respiratory improvement (SpO₂≥94% in room air), sustained until discharge from the hospital or the end of the study (Day 28). Median time to respiratory improvement was not readily available from the literature. Based on very limited data, it is anticipated that the median time to respiratory improvement for the placebo group is 11 days and PTC299 treatment will decrease it to 8 days, an improvement of 3-days. Subjects will be followed for the fixed amount of time of 28 days from randomization (corresponding to the anticipated improvement rates of 0.829 and 0.912 at Day 28 for placebo and PTC299, respectively). A total of 326 events will provide more than 80%

of power to detect a hazard ratio of 1.38 at two-sided type I error of 0.05. Approximately 380 subjects, in total, will be needed.

8.3. Population for Analyses

Intent-to-treat (ITT) population: will include all randomized subjects. The ITT population will be used in all efficacy analysis and subjects will be grouped based on the arm they are randomized to. In the event that a subject received treatment in the arm different from the one to which he/she was randomized, the subject's efficacy data will be analyzed "as randomized."

Safety population: will include all randomized subjects who received at least one dose of study drug. In the event that a subject received treatment in the arm different from the one to which he/she was randomized, the subject's safety data will be analyzed "as treated." The Safety Analysis population will be used in the statistical analyses for safety.

PK population: will include safety population subjects who had at least one PK profile assessment.

8.4. Statistical Analyses

8.4.1. General Approach

For continuous variables, median, mean, standard deviation, minimum, maximum, and the number of subjects with non-missing data will be provided for each treatment group. For categorical variables, the number (percent) of subjects in each category will be provided.

8.4.2. Analysis of Primary Efficacy Endpoints

The primary endpoint is time from randomization to respiratory improvement, defined as SpO₂ \geq 94% on room air sustained until discharge from the hospital or the end of the study (Day 28).

All hospitalized subjects will be followed fully to Day 28 with efficacy measurements taken daily unless they die, are lost to follow-up, or withdraw consent. For subjects who are discharged from the hospital prior to Day 28 without achieving respiratory improvement, SpO₂ measurements will be taken daily until Day 28. All measurements recorded will be used for efficacy analysis.

Subjects who achieved $SpO_2 \ge 94\%$ on room air and sustained this to Day 28 or discharge without taking any COVID-19 rescue therapy during the study will be considered as achieving the respiratory improvement event and the event date will be the first date of achieving $SpO_2 \ge 94\%$. Subjects will be censored at Day 28 if any of the following apply:

- randomized but had no follow-up
- took any COVID-19 rescue therapy during the study
- lost to follow-up prior to Day 28
- died prior to Day 28
- withdrew consent prior to Day 28
- had full follow-up without achieving sustained SpO₂ >94%.

Rescue therapy is defined as any additional medication, exclusive of SOC, used to treat a worsening of COVID-19 symptoms and recorded as rescue therapy on the eCRF.

Kaplan-Meier plots of time to respiratory improvement will be presented. Median time to respiratory improvement will be estimated via the Kaplan-Meier product limit method. A two-sided 95% confidence interval (CI) for the median time to respiratory improvement will be computed for PTC299 and placebo cohorts based on a log-log transformed CI for the survivor function S(t). Time to respiratory improvement will be compared between treatment groups using stratified log-rank test.

Hazard ratio and corresponding two-sided 95% CIs will be estimated using a Cox proportional hazards model, with treatment arm as a single covariate, stratified by the stratification factors.

Respiratory improvement rates at Days 7, 14, and 28 will also be estimated using Kaplan-Meier estimates on the time to respiratory improvement curve. Associated two-sided 95% CIs for each treatment group and the difference between the 2 treatment groups will be calculated using Greenwood's formula for variance derivation.

8.4.3. Analysis of Secondary Efficacy Endpoints

Similar to the primary endpoint, Kaplan-Meier estimate, median and rate at Days 7, 14, and 28 will be presented for time from randomization to defervescence (in subjects presenting with fever at enrollment), time from randomization to respiratory rate ≤24 breaths/minute on room air, time from randomization to cough reported as mild or absent (in those with cough at enrollment rated severe or moderate), and time from randomization to dyspnea reported as mild or absent (on a scale of severe, moderate, mild, absent, in those with dyspnea at enrollment rated as severe or moderate).

The proportion of subjects requiring invasive ventilation at any point during the study, subjects requiring supplemental oxygen or non-invasive ventilation at any point in the study in subjects without supplemental oxygen or non-invasive ventilation at baseline, subjects with normalization of the complete blood count, and the number of subjects who died at the end of the study will be summarized by frequency and percent.

The following secondary endpoints will be summarized descriptively

- Reduction in cytokine levels, potentially including IL-2, IL-6, IL-7, IL-17, G-CSF, IP-10, MCP1, MIP1-α, and TNF-α,
- Reduction in levels of acute phase proteins, potentially including ferritin and C-reactive protein, D-dimer, and cardiac troponin,
- Changes in other laboratory parameters including lactate dehydrogenase, prothrombin time, albumin,
- Reduction in viral load, and
- Duration of hospitalization measured in days

8.4.4. Safety Analyses

8.4.4.1. Subject Disposition

The disposition of subjects, including the number of subjects screened, the number of randomized subjects, the number of randomized subjects who received at least 1 dose of study drug, and the number of subjects who prematurely discontinue study drug, as well as the reason for the premature termination, will be tabulated.

8.4.4.2. Medical History and Prior Medication

Medical history and prior medication information will be summarized.

8.4.4.3. Extent of Exposure and Treatment Compliance

The extent of exposure to study medication is defined as the last dose date minus the first dose date + 1 day. Compliance will be assessed in terms of the percentage of drug actually taken relative to the amount that should have been taken during the study. Exposure and compliance will be summarized descriptively.

8.4.4.4. Adverse Events

Summary information (the number and percent of subjects by treatment) will be tabulated for:

- Treatment-emergent adverse events (TEAEs)
- Treatment-related AEs
- TEAEs by severity
- SAEs
- AEs leading to discontinuation
- AESIs

Summaries will be presented by treatment group and categorized by MedDRA System Organ Class and Preferred Term. The frequencies of AEs displayed will be the crude rates that represent the number of subjects experiencing AEs divided by the total number of subjects.

8.4.4.5. Laboratory Parameters

Changes in clinical laboratory tests from baseline (last measurement prior to first dose) and laboratory marked abnormalities using pre-defined abnormality criteria will be descriptively summarized.

8.4.5. Baseline Descriptive Statistics

Demographic and baseline characteristics of subjects (including ordinal scale score (WHO 2020) will be summarized descriptively by means and standard deviations for continuous variables, and frequency distribution for categorical variables. Summaries will be performed based on all randomized subjects.

8.4.6. Planned Interim Analyses

Two interim analyses are planned. The first interim analysis will be conducted when approximately 40 randomized subjects (20 in each arm) have received 14 days of treatment and completed 14 days of follow-up or discontinued due to death, withdrew consent, or were lost-to-follow-up. No formal statistical testing will be performed at the first interim analysis. An independent data safety monitoring board will review the safety data. Enrollment will continue if there are no safety concerns. A second interim analysis will be conducted for futility. It will be performed when 50% of respiratory improvement events have been reached, ie, 163 events have been observed (approximately 190 subjects). Respiratory improvement is defined as SpO₂ > 94% in room air until discharge from the hospital or the end of study (Day28). All subjects who have completed through Day 28, were discharged with SpO₂ >94% on room air, withdrew consent, died, were lost to follow-up, or took any COVID-19 rescue therapy during the study will be included in the interim analysis. Subjects whose primary event cannot be determined at the interim cut, ie, ongoing subjects, will not be included in the interim efficacy analysis. Subjects who died, withdrew consent, were lost to follow-up, or took any COVID-19 rescue therapy will be censored at Day 28. A stratified log-rank test will be performed and the hazard ratio (treatment vs placebo) will be compared with the futility boundary. The trial may be stopped for futility if the hazard ratio is less than 1.091. The futility boundary is based on Lan-DeMets beta spending function (non-binding option) with overall beta of 80%.

The unblinded interim analyses will be conducted by an independent statistician and the results will be only shared with the closed session of the DSMB. DSMB will make the go- or no-go recommendations and only the recommendations will be communicated with the study team. The study team will be kept blinded for results related to the interim analyses.

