### 3. STUDY DESIGN

#### 3.1. Overall Design

This is a randomized, double-blind, placebo-controlled, multicenter, Phase 2/3, 28-day study with safety follow-up by telephone call at Day 60. The study is designed to evaluate the efficacy and safety of PTC299 as compared with placebo in hospitalized adult subjects with confirmed pneumonia, diagnosed with COVID-19, and not requiring mechanical ventilation. All subjects regardless of receiving PTC299 or placebo, will also receive standard of care as defined per local written policies or guidelines. Eligible subjects will be equally (1:1) randomized to one of the two following treatment arms:

Arm A - Subjects in arm A will receive PTC299 200mg twice a day (BID) (morning and evening at approximately 12-hour intervals) on Days 1 to 7 followed by 50 mg QD (in the morning) on Days 8 to 14. Subjects will be followed up to Day 28 with a safety follow-up phone call at Day 60.

Arm B - Subjects in arm B will receive the matching placebo BID (morning and evening at approximately 12-hour intervals) on Days 1 to 7 followed by the matching placebo QD (in the morning) on Days 8 to 14. Subjects will be followed up to Day 28 with a safety follow-up phone call at Day 60.

Randomization will be stratified by the following three stratification factors:

- Age ( $\leq 62$  vs  $> 62$ )
- Remdesivir use (yes vs no)
- Dexamethasone use (yes vs no)

The study is expected to enroll approximately 380 subjects with two planned interim analyses. The first interim analysis is planned when approximately 40 randomized subjects (20 in each arm) have been enrolled and followed to Day 28 or discontinued due to death, or withdrawal consent, or lost-to-follow-up to assess the safety of the study drug. The 2nd interim analysis is planned when approximately 163 events have been observed (approximately 190 subjects have been followed up to 28 days) to assess the futility of the study.

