### 3.6. Sample Size Determination

This is a group sequential design with 2 interim analyses planned. The first interim analysis will only assess the safety and the trial will not be stopped for futility or superiority of efficacy. It will be performed after the first 40 randomized subjects have completed Day 28 or discontinued due to death, or withdrawal consent, or lost-to-follow-up. The second interim analysis is to assess futility and will be performed when 50% of respiratory improvement events have been reached, ie, 163 events have been observed (approximately 190 subjects). Lan-DeMets beta spending function (non-binding option) is used to define the boundary for the 2nd interim futility analysis and the final analysis to ensure the overall beta of 80%.

The sample size was calculated to reflect the primary endpoint of time from randomization to respiratory improvement, which is defined as the time from randomization to respiratory improvement ( $SpO_2 \geq 94\%$  in room air), sustained until discharge from the hospital or the end of the study (Day 28). Median time to respiratory improvement was not readily available from the literature. Based on very limited data, it is anticipated that the median time to respiratory improvement for the placebo group is 11 days and PTC299 treatment will decrease it to 8 days, an improvement of 3 days. Subjects will be followed for the fixed amount of time of 28 days from randomization (corresponding to the anticipated improvement rates of 0.829 and 0.912 at Day 28 for placebo and PTC299, respectively). A total of 326 events will provide more than 80% of power to detect a hazard ratio of 1.38 at two-sided type I error of 0.05. Approximately 380 subjects, in total, will be needed.

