### 3.7. Interim Analyses

Two interim analyses are planned. The first interim analysis will be conducted when 40 randomized subjects (approximately 20 in treatment arm and 20 in placebo arm) have received 14 days of treatment and completed 14 days of follow-up or discontinued due to death, withdrew consent, or were lost-to-follow-up. No formal statistical testing will be performed at the first interim analysis. An independent data safety monitoring board will review the safety data. Enrollment will continue if there are no safety concerns.

The second interim analysis will be conducted for futility. It will be performed when 50% of respiratory improvement events have been reached, ie, 163 events have been observed (approximately 190 subjects). Respiratory improvement is defined as  $SpO_2 \geq 94\%$  in room air until discharge from the hospital or the end of study (Day 28). All subjects who have completed through Day 28, were discharged with  $SpO_2 \geq 94\%$  on room air, withdrew consent, died, were lost to follow-up, or took any COVID-19 rescue therapy during the study will be included in the interim analysis. Subjects whose primary event cannot be determined at the interim cut, i.e., ongoing subjects, will not be included in the interim efficacy analysis. Subjects who died, withdrew consent, were lost to follow-up, or took any COVID-19 rescue therapy will be censored at Day 28. The detailed censoring rules for the primary endpoint are described in Section 4.9.1.

A stratified log-rank test will be performed, and the hazard ratio (treatment vs placebo) will be compared with the futility boundary. The trial may be stopped for futility if the hazard ratio is less than 1.091. The futility boundary is based on Lan-DeMets beta spending function (non-binding option) with overall beta of 80%.

The unblinded interim analyses will be conducted by an independent statistician and the results will be only shared with the closed session of the DSMB. DSMB will make the go- or no-go recommendation and only the recommendation will be communicated to the study team. The study team will be kept blinded for results related to the interim analyses.

For the first and second interim analyses, all safety analyses will be based on safety population and all efficacy analyses will be based on ITT population.

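### The futility interim drops subjects whose outcome is still open instead of censoring them, which pulls the hazard ratio toward 1 when the drug works; the excess false stopping is small at slow accrual and grows with accrual

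*Protocol*

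**What the plan says.** The synopsis, Protocol 8.4.6 and SAP 3.7 give the same rule for the second interim. Subjects enter if they have reached Day 28, or earlier if they were discharged with the saturation threshold met, died, withdrew, were lost or took rescue therapy. For the rest, Protocol 8.4.6 states: "Subjects whose primary event cannot be determined at the interim cut, ie, ongoing subjects, will not be included in the interim efficacy analysis". SAP 3.7 repeats this. The resolved non-events are handled as follows: "Subjects who died, withdrew consent, were lost to follow-up, or took any COVID-19 rescue therapy will be censored at Day 28". The decision rule is "The trial may be stopped for futility if the hazard ratio is less than 1.091", where a ratio above 1 favors PTC299.

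The timing is described in two ways. Protocol 8.2 and 8.4.6 and SAP 3.6 and 3.7 give 163 events, with about 190 subjects in parentheses. SAP 3.1 gives "approximately 163 events have been observed (approximately 190 subjects have been followed up to 28 days) to assess the futility of the study".

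SAP 3.7 also says that interim efficacy analyses use the ITT population, which SAP 4.2.1 defines as everyone randomized. An analysis that leaves out ongoing subjects does not fit that statement.

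**The concern.** Among subjects enrolled less than 28 days before the cut, those who improve quickly are counted as events and those who have not yet improved disappear. That is right truncation: fast improvers enter from both arms, so the arms look more alike than they are.

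Take subjects enrolled 7 days before the cut, with exponential times and the planned medians. By then 1 - 2^(-7/8) = 45.5% of the drug arm and 1 - 2^(-7/11) = 35.7% of the placebo arm have improved. This difference carries the treatment effect, but the subjects who would show it, those still unimproved, are removed. Among those left, the mean time to improvement is 1/λ - 7e^(-7λ)/(1 - e^(-7λ)) with λ = ln 2/median, which gives 3.15 days on drug and 3.24 days on placebo.

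The futility limit assumes an ordinary log-rank or Cox estimate. If the estimate is attenuated under a true benefit, the chance of a no-go recommendation exceeds the design value, and power falls if the recommendation is followed. SAP 4.9.1.1 has no sensitivity analysis that would reveal this.

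**Working it through.** **Inputs from the documents.** Medians 11 days (placebo) and 8 days (PTC299), 28 days of follow-up, Day 28 rates 0.829 and 0.912, 326 final events, about 380 subjects, 1:1 allocation, two-sided 0.05, interim at 163 events, limit 1.091, Lan-DeMets beta spending. The stated overall beta of 80% is read as 80% power, so beta = 0.20.

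**The plan's own figures reproduce.**
- Exponential hazard ratio: 11/8 = 1.375. Day 28 rates: 1 - 2^(-28/11) = 0.829 and 1 - 2^(-28/8) = 0.912, average 0.8705. Then 163/0.8705 = 187 subjects, against about 190 stated.
- Power with 326 events (Schoenfeld): 0.828 at 1.38 and 0.820 at 1.375.
- O'Brien-Fleming-type beta spent at half information: 2(1 - Φ(1.2816/√0.5)) = 0.0699.
- Risk of falling below the limit at a true ratio of 1.375: Φ(ln(1.091/1.375) × √(163/4)) = Φ(-1.477) = 0.0699.

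The limit is therefore a 7.0% false-stop rule for an unselected estimate on 163 events.

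**Assumptions for the simulation.** The documents give no accrual rate, so it was varied from 0.5 to 8 subjects per day (Poisson). Times are exponential with medians 8 and 11. An event is confirmed at discharge, 0 or 3 days after improvement. The cut is at the 163rd confirmed event, with no early death or rescue. There were 8,000 trials of 380 subjects per setting (Monte Carlo standard error about 0.3 points at 7-10% and 0.5 at 23%). Ranges span the two lags.

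| Accrual per day | Mean HR as written | False stop as written | False stop, ongoing censored | Power as written | Power, ongoing censored |
|---|---|---|---|---|---|
| 0.5-1 | 1.36-1.37 | 7.0-7.5% | 6.6-6.9% | 80.5-80.9% | 81.0-81.2% |
| 2 | 1.35 | 8.2-8.5% | 6.6-6.7% | 79.7-80.0% | 81% |
| 4 | 1.32-1.33 | 10.1-11.0% | 6.6-6.7% | 78.0-78.6% | 81% |
| 8 | 1.22-1.25 | 18.0-23.3% | 6.8% | 67.8-72.5% | 80.9% |

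Power assumes the futility rule is followed. With ongoing subjects censored, the mean hazard ratio is 1.375-1.377 throughout. Censoring at the cut or at the last value below 94% gives nearly the same result (1.370-1.377, stopping 6.6-7.1%).

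A second simulation (12,000 trials per rate, no lag) agrees. As written against censored, stopping is 7.8% vs 7.1% at 1/day, 9.1% vs 7.0% at 2/day, 14.0% vs 7.4% at 5/day and 24.5% vs 7.6% at 8/day. About 12, 24, 59 and 95 ongoing subjects are dropped. With a true ratio of 1.0 the estimate stays at 1.00 and stopping stays near 71%, so nothing changes under the null.

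**Early death or rescue (Days 0-14) at 4/day.** With 10% in both arms, stopping is 18-19% as written and 13% with ongoing subjects censored. The remaining gap from 7% is dilution from non-events held to Day 28, which is a separate matter. With 5% on drug and 10% on placebo, stopping is 3.2-3.6% against 2.5-2.6%.

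**The other reading of the trigger.** If the cut waits until 190 subjects have 28 days of follow-up, the hazard ratio is still attenuated (1.31-1.37). More events are then in hand (173 to 289 in the second simulation), and stopping is 5.3-6.7%, below the designed 7.0%.

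**The case against.** The strongest reply is that the effect is small at any accrual the documents suggest. All 380 subjects between version 1.0 (17 April 2020) and version 7.0 (02 June 2021) would be 380/411 = 0.92 per day. Counting only from version 5.0 (08 October 2020) gives 380/237 = 1.6 per day. Version 7.0 was still adding sites and widening eligibility, so even these look like ceilings on the average. At 8 per day, all 380 would enroll in 380/8 = 47.5 days. The pairing of 163 events with about 190 subjects also describes a nearly mature cohort. This stands for average accrual, and the 4 and 8 per day rows should be read as conditional. It does not settle the rate near the interim, because the start date is not given and the average includes the planned halt after 40 subjects.

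Second, the stated trigger is 163 events everywhere, and "approximately 190 subjects have been followed up to 28 days" may mean at most 28 days. That is possible, but the two readings give different stopping risks, so the wording should not be left open.

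Third, the rule is non-binding and the DSMB only recommends. This is correct and limits the harm to power.

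Fourth, a hospitalized subject now at 94% or above is truly undetermined, because improvement must be sustained to discharge or Day 28. That explains why the subject cannot be called an event. It does not justify discarding the days on which the subject was known not to have improved.

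**Conclusion.** The concern holds. The inclusion rule depends on outcome, conflicts with the SAP's own ITT statement for the interim, and does not match the estimate for which 1.091 was derived. Under a true benefit it attenuates the hazard ratio; under no effect it does not.

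The size depends on accrual, which the documents do not state. With a 163-event cut and no early failures, the excess false stopping is under one point at 1 per day or slower, about 2 points at 2 per day, about 4 at 4 per day and 11 to 17 at 8 per day. The power cost is below one point at the slow end. If the interim waits for 190 subjects at Day 28, the designed 7.0% is not exceeded.

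These figures assume exponential times, equal discharge lags of 0 or 3 days in both arms, no relapse below 94% and an unstratified Cox estimate; the enrollment halt was not simulated. Type I error and the final analysis are not affected. The change should be made because it is cheap and removes the dependence on accrual, not because a large error is likely.

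**What to change.** In the synopsis, Protocol 8.4.6 and SAP 3.7, include all randomized subjects in the interim efficacy analysis. Censor those unresolved at the cut at the last assessment on or before it at which they were known to be event-free: the last saturation below 94% on room air, or the last assessment on supplemental oxygen. Leave the Day 28 rule for deaths, rescue, withdrawal and loss as it is. This also brings the analysis into line with the ITT statement in SAP 3.7.

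State one trigger, in the same words, in the protocol and in SAP 3.1, 3.6 and 3.7: either 163 events, or about 190 subjects with 28 days of follow-up.

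The cost is one censoring sentence and one trigger sentence in each document, and one line in the interim program. No new data are needed and the interim is not delayed.

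Limiting the interim to subjects randomized at least 28 days earlier is an alternative only if the look waits for 163 events in that cohort, which delays it by about 16-21 days in the simulated cases. Applied at the ordinary 163-event cut, that cohort holds only about 97-108 events at 4 per day (12% false stopping) and 32-53 at 8 per day (20-25%).
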